2.1.4.2 Adverse events variables

Adverse event observation period

- Pretreatment adverse events are adverse events that developed or worsened or became serious from the signed informed consent date up to first administration of IMP.
- Treatment-emergent adverse events are adverse events that developed or worsened or became serious during the treatment-emergent adverse event period.
- Posttreatment adverse events are adverse events that developed or worsened or became serious during the posttreatment period.

All adverse events (including serious adverse events and adverse events with special interest) will be coded to a lower-level term (LLT), preferred term (PT), high-level term (HLT), high-level group term (HLGT), and associated primary system organ class (SOC) using the version of Medical Dictionary for Regulatory Activities (MedDRA) currently in effect at Sanofi at the time of database lock.

The occurrence of adverse events (including serious adverse events and adverse events with special interest) is recorded from the time of signed informed consent until the end of the study.

Injection site reaction adverse events and hypersensitivity reactions adverse events will be identified using MedDRA searches listed in the ADaM metadata.

Adverse events of special interest include:

- Pregnancy occurring in a female patient entered in the clinical trial.
- Symptomatic overdose (serious or non-serious) with IMP/NIMP (event suspected by the investigator or spontaneously notified by the patient/parent [not based on systematic drug accountability]).
- Unusual lack of efficacy of IMR (Canada only).

2.1.4.3 Deaths

The deaths observation period are per the observation periods defined above.

- Death on-study: deaths occurring during the on-study observation period (defined as the time from the signed informed consent date up to the end of the study, ie, last protocol planned visit or the resolution/stabilization of all SAEs).
- Death pretreatment: deaths occurring before the on-study observation period.
- Death on-treatment: deaths occurring during the on-treatment period.
- Death post study: death occurring after the end of study.

2.1.4.4 Laboratory safety variables

Clinical laboratory data consists of blood analysis, including hematology, clinical chemistry, and urinalysis. Clinical laboratory values after conversion will be describe into standard international units and international units will be used in all listings and tables.

Blood samples for clinical laboratories will be taken at screening visit (Visit 1 – Week -2) for identifying patients with exclusion criteria or safety consideration and will be test at screening visit. The laboratory parameters will be classified as follows:

- Hematology,
 - Erythrocytes, hemoglobin, hematocrit, leukocytes and platelets;
- Clinical chemistry,
 - Sodium, potassium, uric acid, creatinine, estimated creatinine clearance, eGFR (derived), alanine aminotransferase (ALT), aspartate aminotransferase (AST), alkaline phosphatase (ALP), total and conjugated bilirubin;

- Urine samples will be collected as follows:
 - Urinalysis - quantitative analyses: pH, glucose, ketones, leucocytes, blood/hemoglobin, protein.

Technical formulas are described in [Section 2.5.1](#).

2.1.4.5 Vital signs variables

Vital signs include: heart rate (bpm), sitting systolic and diastolic blood pressure (mmHg) as well as body weight (kg).

2.1.4.6 Electrocardiogram variables

Not applicable.

2.1.5 Pharmacokinetic variables

Not applicable

2.1.6 Pharmacodynamic/genomics endpoints

Not applicable

2.1.7 Patient reported outcome endpoints

All the following endpoints are considered as secondary endpoints.

All PROs will be administered electronically using mobile technology.

2.1.7.1 Study methodology endpoints: Patient satisfaction with trial experience (WIWI)

Patient satisfaction with trial experience will be measured using the Was It Worth It (WIWI) Questionnaire, completed at Week 24 (Visit 12). The WIWI has 5 items, each with a 3-level categorical response scale. Each item is scored separately.

See questionnaire in [Appendix C](#).

2.1.7.2 Study methodology endpoints: Impact of trial participation (WPAI)

The effect of the trial on a patients' ability to work and perform regular activities will be measured using an adaptation of the Work Productivity and Impairment (WPAI) Questionnaire, administered at baseline and Week 24 (Visit 12).

The WPAI-SP has 6 items, and scoring follows that of the WPAI-SHP. As such, each item is presented separately, expressed as impairment percentages, with higher numbers indicating

greater impairment and less productivity, ie, worse outcomes. In addition, the following combined items will be reported:

- the percent work time missed due to study participation [$Q2/(Q2 + Q4)$].
- the percent impairment while working due to study participation [$Q5/10$].
- the percent overall work impairment due to study participation [$Q2/(Q2 + Q4) + (1 - (Q2/(Q2 + Q4))) \times (Q5/10)$].
- the percent activity impairment due to study participation [$Q6/10$].

See questionnaire in [Appendix D](#).

2.1.7.3 Study methodology endpoints: Patient burden with trial participation (OSEP)

Patient burden with trial participation will be measured using a new PRO: the Overall Study Experience-Participation (OSEP) Questionnaire. Each item will be scored separately. The OSEP has 2 parts:

- OSEP Part 1 contains 4 items to examine perceptions of diabetes control; it will be administered at baseline and Week 24 (Visit 12).
- OSEP Part 2 contains 9 items to examine perceptions of study participation; it will be administered only at Week 24 (Visit 12).

See questionnaire in [Appendix E](#).

2.1.7.4 Study methodology endpoints: Resource use (RUQ)

Healthcare resource use will be measured using a new PRO: the resource use questionnaire (RUQ). The RUQ will be administered every 4 weeks from baseline to Week 24. The RUQ asks the patients to report the resources used (time and expenses) during the previous 4 weeks in terms of visits to healthcare professionals.

See questionnaire in [Appendix F](#).

2.1.7.5 Diabetes control endpoints: Diabetes-related patient reported outcomes (DTSQs, DTSQc, HFS-II, DDS)

Diabetes Treatment Satisfaction Questionnaire (DTSQ)

Treatment satisfaction will be measured with the Diabetes Treatment Satisfaction Questionnaire (DTSQ). The DTSQ is available in two versions:

- The DTSQ status (DTSQs) version evaluates absolute treatment satisfaction in the “past few weeks” and will be administered at baseline and Week 24 (Visit 12).

- The DTSQ change (DTSQc) version measures the relative change in treatment satisfaction from previous therapy and will be administered (after the DTSQs) at Week 24 (Visit 12) only.

The DTSQs and DTSQc conceptually contain the same 8 items, each scored on a 7-point scale but with different response options. Six items are summed to produce a measure of treatment satisfaction, with total scores ranging from 0 (very dissatisfied) to 36 (very satisfied) for the DTSQs and -18 (much less satisfied) to +18 (much more satisfied) on the DTSQc. The remaining 2 items, which measure perceived frequency of hyperglycemia and perceived frequency of hypoglycemia, are treated independently. These items are scored on a scale ranging from 0 (none of the time) to 6 (most of the time) on the DTSQs and -3 (much less of the time now) to +3 (much more of the time now) on the DTSQc.

See questionnaire in [Appendix G](#) and [Appendix H](#).

Hypoglycemia Fear Survey-II (HFS-II)

Fear of hypoglycemia will be measured with the Hypoglycemia Fear Survey-II (HFS-II) at baseline and Week 24 (Visit 12). The HFS-II comprises 33 items:

- The hypoglycemia fear survey-behavior subscale [HFS-B]: 15 items explore behaviors that patients may engage in to avoid low blood sugar and its negative consequences.
- The hypoglycemia fear survey-worry subscale [HFS-W]: 18 items relate to concerns that patients may have about their hypoglycemia.
- HFS-total score : all 33 items.

Responses are made on a 5-point Likert scale where 0 = “Never” and 4 = “Always” with a past 3 months recall period.

Higher total score reflects greater fear of hypoglycemia. A higher Behavior score reflects greater tendency to avoid hypoglycemia and/or its negative consequences. A higher Worry score reflects higher worry concerning episodes of hypoglycemia and its consequences.

See questionnaire in [Appendix I](#).

Diabetes Distress Scale (DDS)

Diabetes-related distress will be measured using the Diabetes Distress Scale (DDS) at baseline and Week 24 (Visit 12).

The DDS contains 17 items related to potential problem areas that people with diabetes may experience. Patients are asked to consider the degree to which each of the items may have distressed or bothered them during the past month, and respond between 1 (not a problem) and 6 (a very serious problem).

The DDS yields a total diabetes distress score and 4 subscale scores, each addressing a different kind of distress (emotional burden, physician distress, regimen distress, interpersonal distress).

Each score (total and subscales) are presented as an average, by summing the patient's responses to the appropriate items and divide by the number of items in that scale.

In addition, total and subscale scores will be categorized: a mean score 2.0 – 2.9 should be considered 'moderate distress' and a mean score >3.0 should be considered 'high distress'.

See questionnaire in [Appendix J](#).

2.1.8 Investigator (clinician) reported outcome (ClinRO) endpoints

Overall Study Experience-sites (OSES) questionnaire

Site investigators (one per site) will be asked to complete the Overall Study Experience-sites (OSES) questionnaire. The OSES has 2 parts:

- OSES Part 1 contains 1 item to examine resource requirements: "Approximately how much time did you spend with this participant (in person or via phone) during this scheduled visit/communication?". OSES Part 1 will be administered following each study visit.
- OSES Part 2 contains 2 items to examine relationship ("I had a good relationship with this patient during the study") and satisfaction with care ("I am satisfied with the level of care I have provided for this participant in this study"). OSES Part 2 will be administered at Week 24 (Visit 12) only.

Each item is scored separately.

See questionnaire in [Appendix K](#).

2.1.9 Health economic endpoints

Not applicable

2.1.10 Patient interviews

English-speaking patients of the virtual group who consent will be invited to participate in interviews following their Week 24 (Visit 12) study visit (ie, after completion of the trial). These qualitative exit interviews will be conducted one-on-one with up to 30 patients to:

- Examine patients' experiences of trial participation, in their own words.
- Explore the positive and negative aspects of trial participation.
- Provide some context to responses given in the PRO questionnaires.

Analysis plan and analysis report will be performed and details by an external vendor in specific separate documents.

2.2 DISPOSITION OF PATIENTS

This section describes patient disposition for both patient study status and the patient analysis populations.

Screened patients are defined as any patients who met the inclusion criteria and signed the informed consent.

Randomized patients consist of all patients with a signed informed consent form who have had a treatment kit number allocated and recorded in the IRT database, regardless of whether the treatment kit was used.

For patient study status, the total number of patients in each of the following categories will be presented in the clinical study report using a flowchart diagram or summary table:

- Screened patients.
- Screen failure patients and reasons for screen failure.
- Non randomized but treated patients.
- Randomized patients.
- Randomized but not treated patients.
- Randomized and treated patients.
- The intent-to-treat (ITT) population [Section 2.3.1.1](#)) analyzed as randomized.
- The randomization strata (sites and screening HbA1c categories [$<7.6\%$, $\geq 7.6\%$] assigned by IRT); the discrepancy between the strata assigned by IRT and the information reported on e-CRF will be listed for all randomized patients.
- Patients who completed the 24-week treatment period (patients who have attended Visit 12 [Week 24] and who did not permanently discontinue treatment).
- Patients who permanently discontinued the IMP during the 24-week treatment period, and the reasons for permanent treatment discontinuation.
- Patients who completed the 24-week study period (patients who have performed Visit 12 [Week 24], whichever the treatment duration).
- Patients who discontinued the study during the 24-week period, and the reason for study discontinuation.
- Patient's decision for treatment discontinuation decision for treatment discontinuation during the 24-week period.
- Status at last study contact.

For all categories of patients (except for the screened and nonrandomized categories) percentages will be calculated using the number of randomized patients as denominator for different study conduct approach groups. Reasons for treatment discontinuation will be supplied in tables giving numbers and percentages by study conduct approach group.

Reasons for treatment discontinuation will be supplied in tables giving numbers and percentages by study conduct approach group. A listing of patients who prematurely discontinued study treatment with further reason (“other reason”) provided in free text will be provided.

Patients with the following deviations will be identified and described in separate listings:

- Treated but not randomized.
- Randomized but not treated.
- Randomized but allocated to one approach (virtual or traditional) by randomization, and actually switched of study conduct approach.

A list of patients who prematurely discontinued the treatment, along with reasons for discontinuation, will be provided.

Kaplan-Meier (KM) plots/estimates of the cumulative incidence of IMP discontinuation due to any reason, or due to AE, will be provided for the 24-week on-treatment period separately. Time to treatment discontinuation will be defined as the number of days from the first dose of IMP until the day of treatment discontinuation. All completers will be considered as censored observations. The censoring time will be the number of days from the first dose of IMP until the last dosing date.

All critical or major deviations potentially impacting efficacy analyses, randomization, and drug-dispensing irregularities, and other major or critical deviations will be summarized in tables giving numbers and percentages of deviations by study conduct approach group.

Additionally, the analysis populations for safety, efficacy will be summarized in a table by number of patients on the randomized population.

- Efficacy population: intent-to-treat (ITT) population.
- Safety population.

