1.2 STUDY FLOW CHART

(☎ = virtual visits; 📞 = phone call visits; P = on-site in-person visits)

Visits	Screening		Randomization		Treatment period										Follow-up
	1 Step-1 ^a	1 Step-2 ^b	2 Step-1 ^c	2 Step-2 ^d	3	4	5	6	7	8	9	10	11	12 EOT ^g	13 EOS
Traditional group	☎ (Digital screening)		📞	P	📞	📞	📞	P	📞	P	📞	P	📞	P	📞
Virtual group	☎ (Digital screening)		📞	P & ☎	☎	☎	☎	☎	☎	☎	☎	☎	☎	☎	☎
Weeks	-3	-2	-1	0	1	2	3	4	6	8	12	16	20	24	1 week
Window (day)			-/+ 4		-/+ 3	-/+ 3	-/+ 3	-/+ 4	-/+ 3	-/+ 4	-/+ 3	-/+ 4	-/+ 3	-/+ 3	+/-2
Informed Consent (eConsent)	X														
Schedule Homecare visit	X														
Interactive response technology (IRT) calls	X		X				X		X		X		X		
Inclusion	X	X													
Exclusion		X													
Demography	X	X													
Video chat with Investigator and site staff	X	X													
Medical and surgical history; diabetes history		X													
Concomitant medication(s)		X		X	X	X	X	X	X	X	X	X	X	X	X
Physical examination ^d				X											
Vital signs ^h and body weight		X		X			X		X		X		X		
Height		X													
Virtual material/device shipment (Bluetooth devices) ^e			X												
Dispensation/collection of e-diary				X	X	X	X	X	X	X	X	X	X	X	

Visits	Screening		Randomization		Treatment period										Follow-up
	1 Step-1 ^a	1 Step-2 ^b	2 Step-1 ^c	2 Step-2 ^d	3	4	5	6	7	8	9	10	11	12 EOT ^g	13 EOS
Traditional group	Ⓢ (Digital screening)		☎	P	☎	☎	☎	P	☎	P	☎	P	☎	P	☎
Virtual group			☎	P & Ⓢ	Ⓢ	Ⓢ	Ⓢ	Ⓢ	Ⓢ	Ⓢ	Ⓢ	Ⓢ	Ⓢ	Ⓢ	Ⓢ
Weeks	-3	-2	-1	0	1	2	3	4	6	8	12	16	20	24	1 week
Window (day)			-/+ 4		-/+ 3	-/+ 3	-/+ 3	-/+ 4	-/+ 3	-/+ 4	-/+ 3	-/+ 4	-/+ 3	-/+ 3	+/-2
Randomization via IRT call			X												
Video chat with investigator and site staff via the virtual device ^e				X	X	X	X	X	X	X	X	X	X	X	X
Allocation of study medication (IMP)				X				X		X		X			
First IMP (Toujeo) injection ^e				X											
Documentation and review of IMP and NIMP doses ^f				X	X	X	X	X	X	X	X	X	X	X	
IMP compliance check; collecting & counting used & unused pens								X		X		X		X	
Diet and lifestyle counselling		X		X	X	X	X	X	X	X	X	X	X		
Glucose meter shipment ^c			X												
7-Point SMPG ⁱ				X								X		X	
5-point SMPG ⁱ				X	X	X	X	X	X	X	X	X	X	X	
Upload SMPG to PC ^j				X				X		X		X		X	
AE/SAE	To be assessed and reported (if any) since consent throughout the study (report SAE to the sponsor within 24 hours)														
Hypoglycemia recording	To be assessed and reported (if any) since randomization throughout the study														

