8.4 METHOD OF ASSIGNING PATIENTS TO GROUP

There is only one study medication provided in open-label boxes for all randomized patients. Boxes will be individually identified with treatment kit numbers. The nonrandomized sequential treatment kit number list will be generated centrally by Sanofi. The study medication will be packaged in accordance with this list.

The Study Biostatistician will provide the randomization scheme (including stratification) to the centralized randomization system (IRT). Then, the IRT generates the patient randomization list according to which it allocates study approach to the patients.

At screening (Visit 1 – Step 1), the investigator or designee will contact the IRT system to receive the patient number. The patient identification (patient number) is composed of 12-digits (3-digit country code, 4-digit center code, and 5-digit patient chronological number). If a patient who had previously failed screening is approached for rescreening, a new informed consent form must be signed. In such case, a new patient number will be assigned by IRT.

Patients will be randomized in a 1:1 ratio to either virtual or traditional study conduct approach.

Randomization will be stratified by HbA1c obtained at the screening visit (<7.6%; ≥7.6%) and study site (see rationale in [Section 6.1](#)).

On Visit 2-Step 1, the IRT will be contacted for randomization and for first treatment kit(s) allocation. The investigator or designee will have to call the IRT to provide some information (such as patient number provided by IRT at screening visit, date of birth, etc). Afterwards the IRT will be called again each time a new treatment kit(s) allocation is necessary, ie, the visits as indicated in the study flowchart ([Section 1.2](#)).

A randomized patient is a patient who has been allocated to a randomized trial approach by the IRT, regardless whether Toujeo treatment kit was provided and used or not.

A patient cannot be randomized more than once in the study.

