11.2 DISPOSITION OF PATIENTS

Screened patients are defined as any patient who met the inclusion criteria and signed the informed consent.

Randomized patients consist of all screened patients with a trial approach group allocated and recorded in the IRT database, regardless of whether the treatment kit was used or not.

For any patient randomized more than once, only the data associated with the first randomization will be used in any analysis population. The safety experience associated with any later randomization will be assessed separately.

The safety experience of patients treated and not randomized will be reported separately, and these patients will not be in the safety population.

The total number of patients for each of the following categories will be presented.

- Screened patients
- Screen failure patients and reason for screen failure
- Randomized patients
- Safety population ([Section 11.3.2](#)) presented as treated
- The intent-to-treat (ITT) population ([Section 11.3.1](#)) analyzed as randomized
- The randomization strata (sites and screening HbA1c categories [$<7.6\%$, $\geq 7.6\%$] assigned by IRT); the discrepancy between the strata assigned by IRT and the information reported on e-CRF will be listed for all randomized patients

- Patients who permanently discontinued the IMP, and the reasons for permanent treatment discontinuation
- Patients who completed the 24-week treatment period (patients who have attended Visit 12, who did not permanently discontinue treatment, and who did not take any rescue medication)
- Patients who did not complete the 24-week treatment period
- Patients who discontinued 24-week treatment by main reason for permanent treatment discontinuation
- Patients who completed the study (patients who have attended Visit 12, whichever the treatment duration)
- Patients who did not complete the study (patients who have not attended Visit 12)
- Patients who discontinued the study by main reason for study discontinuation

For all categories of patients except screened and screen failure patients, percentages will be calculated using the number of randomized patients as denominator for each approach group.

Patients with the following deviations will be identified and described in separate listings:

- Treated but not randomized
- Randomized but not treated
- Randomized but not treated as randomized

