2.2.1 Randomization and drug dispensing irregularities

Randomization and drug-dispensing irregularities occur whenever:

1. A randomization is not in accordance with the protocol-defined randomization method, such as a) an ineligible patient is randomized, b) a patient is randomized based on an incorrect stratum, c) a patient is randomized twice, or d) in a dynamic randomization scheme the treatment assignment is, in fact, not random, due to a computer program error.

OR

2. A patient is dispensed an IMP kit not allocated by the protocol-defined randomization, such as a) a patient at any time in the study is dispensed a different treatment kit than as randomized (which may or may not contain the correct-as-randomized IMP), or b) a nonrandomized patient is treated with IMP reserved for randomized patients.

Randomization and drug-dispensing irregularities will be monitored throughout the study and reviewed on an ongoing basis.

All randomization and drug-dispensing irregularities will be documented in the clinical study report. If the number of irregularities is large enough to make a tabular summary useful, the irregularities will be categorized and summarized among randomized patients (number and percentages). Nonrandomized, treated patients will be described separately.

Randomization and drug-dispensing irregularities to be prospectively identified include but are not limited to:

- Kit dispensation without IRT transaction.
- Erroneous kit dispensation.
- Kit not available.
- Randomization by error.
- Patient randomized twice.
- Forced randomization.
- Stratification error.
- Patient switched to another site.

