2.3 ANALYSIS POPULATIONS

Patients treated without or before being randomized will not be considered randomized and will not be included in any efficacy population.

The randomized population includes any patient who has been allocated to a study conduct approach group regardless of whether the study conduct approach group is followed.

For any patient randomized more than once, only the data associated with the first randomization will be used in any analysis population. The safety experience associated with any later randomization will be assessed separately.

The safety experience of patients treated and not randomized will be reported separately, and these patients will not be in the safety population.

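### SAP 2.2 counts randomized patients by treatment kit number, although the trial randomizes the study approach; the disposition and withdrawal denominators should follow the IRT approach allocation instead

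*SAP*

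**What the plan says.** - **SAP 2.2 (disposition)** defines randomized patients as those with signed consent "who have had a treatment kit number allocated and recorded in the IRT database, regardless of whether the treatment kit was used". It then uses the number randomized as the denominator for percentages in each approach group.
- **Protocol 8.4** says: "A randomized patient is a patient who has been allocated to a randomized trial approach by the IRT, regardless whether Toujeo treatment kit was provided"; whether the patient used a kit is likewise irrelevant. The same section explains that kits carry no randomized information: "The nonrandomized sequential treatment kit number list will be generated centrally by Sanofi".
- **Protocol 11.2**, which SAP 2.2 corresponds to, says: "Randomized patients consist of all screened patients with a trial approach group allocated and recorded in the IRT database".
- **SAP 2.3 (analysis populations)** agrees with the protocol: "The randomized population includes any patient who has been allocated to a study conduct approach group". SAP 2.3.1 takes ITT from the protocol, and SAP 2.3.1.1 makes it all randomized patients, analyzed by allocated approach.
- **SAP 2.4.3.4** sends the description of patient withdrawal back to SAP 2.2.
- **SAP 1.5 and 1.6** declare no modification of the protocol's statistical section.

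**The concern.** The kit-based sentence would suit a trial in which the kit carries the randomized treatment. Here a kit number says nothing about the arm, and a patient is randomized once the IRT has assigned an approach. The SAP therefore holds two incompatible definitions, and the one in SAP 2.2 departs from the protocol without being declared.

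Retention under the two approaches is a secondary objective, and SAP 2.2 is where its counts are produced. A patient who is assigned an approach, learns which one, and leaves with no kit number recorded is relevant to the comparison. Under protocol 11.2 that patient is in the denominator as randomized but not treated. Under SAP 2.2 as written the patient is not counted at all.

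**Working it through.** **1. The plan's own figure.** The only planning figure is a 95% CI half-width of about 0.37% for HbA1c change (protocol 11.1), with SD 1.1 and up to 10% non-evaluable. Evaluable per arm: 75 × 0.90 = 67.5. Half-width of the difference: 1.96 × 1.1 × √(2/67.5) = 0.371, which reproduces it. Correcting the definition leaves the planned 150 and this figure unchanged. Even if one evaluable patient were lost from one arm, the result would be 1.96 × 1.1 × √(1/67.5 + 1/66.5) = 0.373. The point does not concern precision.

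**2. The definitions side by side.**

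| Place | What makes a patient randomized | Kit number needed? |
|---|---|---|
| Protocol 8.4 | Approach allocated by IRT | No, stated explicitly |
| Protocol 11.2 | Approach allocated and recorded in IRT | No |
| SAP 2.3 | Approach allocated | No |
| SAP 2.2 | Kit number allocated and recorded in IRT | Yes |

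The definitions differ only for a patient with an approach on record and no kit number.

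**3. Can such a patient arise?** There are two routes.

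- *Irregularity.* SAP 2.2.1 lists "Kit not available" among the events to be identified. It does not say whether a number would still be recorded, or whether the first kit is meant.
- *Timing.* Protocol 8.4 says: "On Visit 2-Step 1, the IRT will be contacted for randomization and for first treatment kit(s) allocation". On that text the interval between approach and kit number is zero. The flow chart (protocol 1.2, repeated in SAP Appendix B) places the randomization call at Visit 2-Step 1 but marks study medication allocation at Visit 2-Step 2. Protocol 8.1.5 puts that visit 7 ± 4 days after the randomization call. Taken literally, the interval is 7 − 4 = 3 to 7 + 4 = 11 days.

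**4. Which outputs depend on SAP 2.2?** The disposition percentages do, directly. So does patient withdrawal, through SAP 2.4.3.4. ITT is governed by SAP 2.3 to 2.3.1.1, which use the approach.

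**5. Size per patient.** SAP 2 reports 15 randomized of 150 planned. It does not say which definition produced the 15; I take it to be the protocol's.

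- As planned: 1/150 = 0.67% of all patients, or 1/75 = 1.3% of an arm.
- As recruited: 1/15 = 6.7% of all patients.
- Within an arm the split is not given. If it were 7 and 8 (an assumption), one patient would be 1/8 = 12.5% to 1/7 = 14.3%.

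As an illustration only, suppose one of the 15 left without a kit number and the other 14 completed. Completion would be 14/15 = 93.3% under protocol 11.2 and 14/14 = 100% under SAP 2.2.

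**The case against.** The strongest reply is that this is leftover wording with little practical effect. Much of that stands.

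- *ITT.* A reader might infer that patients drop out of the ITT population. The SAP as a whole does not support this. SAP 2.3 defines the randomized population by approach and SAP 2.3.1 defers to the protocol, so an analyst would have to override both with a disposition sentence. A patient who leaves before any kit would also normally have no Week 16 or Week 24 HbA1c to contribute.
- *Arm difference.* A reader might also infer a larger loss in the traditional arm, because its patients receive insulin at Visit 2-Step 2 while virtual patients have it shipped beforehand. Those are delivery times. SAP 2.2 asks for a number recorded in the IRT, and protocol 8.4 assigns it at the randomization contact in both arms.
- *The 3 to 11 days.* The flow chart shows no IRT call at Visit 2-Step 2 (column alignment in the extracted table is imperfect, but both copies agree on this). Its allocation visits match the supply visits in protocol 8.1.3. Virtual patients must already hold insulin by then. The row may therefore describe supply, and the interval is conditional.
- *Withdrawal endpoint.* It runs from Day 1, the first injection, so someone who never received a kit may not count as a withdrawal event. SAP 2.5.4 sets Day 1 at randomization for untreated patients, but for visit windows. This narrows the effect mainly to the denominator.
- *Early termination.* Only basic descriptive output is now planned, and SAP 2.2.1 requires irregularities to be documented in the study report.

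None of this reconciles SAP 2.2 with SAP 2.3. In a purely descriptive report of 15 patients, counts and denominators are much of the result.

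**Conclusion.** The point holds as an undeclared contradiction within the SAP and with the protocol, with a conditional effect on disposition and withdrawal denominators by group. The effect requires a patient with an approach allocated and no kit number recorded, through an irregularity or the flow-chart timing taken literally, and a programmer who applies SAP 2.2 as written. Each such patient would be 6.7% of those randomized, taking the 15 as counted under the protocol's definition.

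The documents do not show that any patient was affected, that a loss would differ by arm, or that the HbA1c analysis would change. The correction is worthwhile because the sentence is wrong for this design and costs almost nothing to put right.

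**What to change.** Replace the SAP 2.2 sentence with the protocol 11.2 definition: randomized patients are all screened patients whose approach group has been allocated and recorded in the IRT, whether or not a kit number was allocated or used. A patient with an approach but no kit then falls under randomized but not treated, a category SAP 2.2 already lists.

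Separately, reconcile protocol 8.4 with the flow chart in protocol 1.2 and SAP Appendix B on when the first kit is allocated, and make clear whether the flow-chart row means IRT allocation or supply.

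The SAP change is one sentence and the timing point a short clarification. Neither alters the sample size, the models or data collection. Before reporting, check the IRT records for any patient with an approach and no kit number; with 15 randomized this is a brief task and would settle whether the point had any effect.
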